2.3.2 POTENTIAL BENEFITS

Metformin may improve the risk of diabetes and improve features of the metabolic syndrome.

Potential benefits of the proposed research to participants and others

In principle, participants will not derive any benefits from participation in the study. However, participants will undergo actionable blood tests at screening and during follow-up that might uncover an underlying medical problem not related to the study that might otherwise gone unnoticed. We will share study results with participants, who in turn will be able to share the results with their physicians. If participants do not have a primary physician and need guidance, the site PIs will facilitate referral to a primary care physician at each of the study sites. The results of brain MRI will not be shared with participants. However, if there are level 3 or 4 findings, participants will be notified as soon as possible by the pertinent site PI or designated physician. Level 3 findings require evaluation that is not urgent. Level 4 findings require urgent evaluation and possibly an immediate emergency room referral. Participants on metformin may derive metabolic benefits and desired weight loss from participation in the study. The benefit to others comes from learning about whether metformin can prevent Alzheimer's dementia.

Importance of the knowledge to be gained

MAP is responsive to NIA's Funding Opportunity Announcement PAR-18-028 "Phase III Clinical Trials for the Spectrum of Alzheimer's Disease and Age-related Cognitive Decline". MAP addresses the following example of interventions listed in PAR-18-028 "repurposed drugs that have promise for AD treatment such as chemotherapeutic agents or drugs for insulin dysregulation/diabetes. MAP is responsive to goal 1 of the National Plan to Address Alzheimer's Disease to "Prevent and Effectively Treat Alzheimer's Disease and Related Dementia by 2025". There are no known preventive or curative strategies for Alzheimer's disease at the moment. Recent clinical trials of amyloid based therapies have failed. MAP provides an opportunity to test a medication that has metabolic benefits and a low-risk side effect profile for the prevention of the cognitive declines associated with conversion to Alzheimer's dementia among persons with prodromal Alzheimer's dementia.

3 OBJECTIVES AND ENDPOINTS

OBJECTIVES	ENDPOINTS	JUSTIFICATION FOR ENDPOINTS
Primary		
1. To compare changes from baseline to 18 months in verbal memory performance, measured with the Total Recall Score of the FC-SRT, between the metformin and placebo arms, following an ITT approach.	Changes in Total Recall Score of the Free and Cued Selective Reminding Test (FC-SRT)	The justification for using the FC-SRT as the primary outcome is that a similar test of verbal learning, the SRT, was the co-primary outcome in the MetMCI study that demonstrated a difference between the metformin and placebo arms. The FC-SRT is a more advanced version of the SRT that is sensitive to memory changes in prodromal Alzheimer's disease. ¹³²
Secondary		
1. We will examine global cognitive performance, measured with the ADCS-PACC, as a secondary outcome.	Changes from baseline to 18 months in global cognitive performance, measured with the ADCS-PACC score, a composite that includes 4 tests: The FC-SRT, 2. The Delayed Recall score on the Logical Memory IIa subtest from the Wechsler Memory Scale, The Digit Symbol Substitution Test score, from the Wechsler Adult Intelligence Scale-Revised, and the Mini Mental Status total score.	The ADCS-PACC is being used in clinical trials in persons with prodromal AD.
2. To compare changes in neurodegeneration, ascertained as cortical thickness ascertained on brain MRI from baseline to 18 months between metformin and placebo.	Changes from baseline to 18 months in cortical thickness ascertained on brain MRI	Cortical thickness is a measure of neurodegeneration.
3. To compare changes in cerebrovascular disease, ascertained as WMH volume on brain MRI, from baseline	Changes in from baseline to 18 months in cerebrovascular disease, ascertained as white matter	WMH is a measure of cerebrovascular disease.

OBJECTIVES	ENDPOINTS	JUSTIFICATION FOR ENDPOINTS
to 18 months between metformin and placebo.	hyperintensities (WMH) volume (in mL) on brain MRI.	
4. To compare changes in brain amyloid from baseline to 18 months between the metformin and placebo arms.	Changes from baseline to 18 months in whole brain Ab standardized uptake value ratio (SUVR) and in incident amyloid positivity	whole brain Ab SUVR is a marker of in-vivo brain amyloid burden
5. To compare changes in brain tau burden from baseline to 18 months between the metformin and placebo arms.	Changes from baseline to 18 months in tau SUVR in a composite brain region comprising medial and inferolateral temporal cortex	tau SUVR in a composite brain region is a biomarker of in-vivo brain tau
6. To compare changes in AD plasma biomarkers, between metformin and placebo during follow-up	Changes from baseline to 18 months in plasma AD biomarkers. These biomarkers will be measured in plasma from baseline and months 6, 12 and 18	AD plasma biomarkers are markers of neuropathology.
Exploratory		
1. To examine APOE- ϵ 4 genotype and COVID 19 history as a modifier of the interventions.	All outcomes listed above. Persons without an APOE- ϵ 4 allele will be compared with those homozygous or heterozygous for APOE- ϵ 4. COVID-19 history will be ascertained by self-report.	Primary and secondary endpoints. Previous studies have demonstrated a higher risk of dementia among persons with hyperinsulinemia who are heterozygous or homozygous for APOE- ϵ 4. COVID-19 may cause long term cognitive sequelae that could affect the effectiveness of metformin.

4 STUDY DESIGN

4.1 OVERALL DESIGN

We propose to conduct a phase II/III, multisite 1:1 randomized double-blinded placebo-controlled trial of extended-release metformin (maximum dose of 2,000 mg, four Glucophage XR® 500 mg tabs [reduced mass]) in 326 men and women, aged 55 to 90 years of age, with amnestic mild cognitive impairment (including early and late amnestic mild cognitive impairment). The trial will last 18 months. After screening for eligibility and consent, participants will have a baseline visit, followed by randomization to metformin or matching placebo, and a titration phase. Metformin (or matching placebo) will be titrated from 500 mg a day to 2,000 mg a day at increments of 500 mg every 10 days, as recommended by the manufacturers. Participants will be seen every 6 months thereafter for study assessments. Study procedures will include phlebotomy and laboratory tests, general health questionnaires,

neuropsychological testing, physical exam comprising a brief neurologic exam, measurement of vital signs and anthropometric measures. Study partners will also undergo questionnaires. Up to 186 participants will undergo brain magnetic resonance imaging (MRI) before IP is initiated (a window of two months is allowed to complete brain imaging), and after the last assessment at 18 months. Similarly, up to 186 participants will undergo amyloid and tau Positron Emission Tomography (PET). MAP will be a multisite study.

4.2 SCIENTIFIC RATIONALE FOR STUDY DESIGN

Alzheimer's dementia is a common disease with no current cure. One in ten Americans over the age of 65 years will develop Alzheimer's dementia. Participation in this study will help advance knowledge of this disease. It is unknown if metformin will prevent cognitive decline associated with Alzheimer's dementia. A control group administered placebo is necessary to determine if changes in verbal memory performance, as measured with the FC-SRT and global cognitive performance, as measured with the ADCS-PACC, are related to the use of metformin or not. The placebo control group will not be subject to risks greater than the intervention arm.

4.3 JUSTIFICATION FOR DOSE

The justification for the dose is that it is the maximum approved dose for the treatment of diabetes, also used off label for diabetes prevention among persons at risk.

4.4 END OF STUDY DEFINITION

A participant is considered to have completed the study if he or she has completed all phases of the study including the last visit or the last scheduled procedure shown in the flow diagram in Section 1.2 Schema. The end of the study is defined as completion of the last visit or procedure by all participants.

5 STUDY POPULATION

5.1 INCLUSION CRITERIA

- Diagnosis of aMCI: in general, the diagnosis of aMCI follows the definition in the 2011 National Institute on Aging (NIA)/ Alzheimer's association (AA) guidelines, without biomarkers.¹³³ Participants must have:
 - Subjective memory concerns reported by the participant, study partner, or clinician.
 - A mini-mental state exam ≥ 22 for participants with more than 8 years of education. For participants with less than 8 years of education, a MMSE ≥ 20 will be allowed.
 - Clinical Dementia Rating (CDR) = 0.5. The memory box score must be at least 0.5. Information from the formal University of Washington CDR instrument, report by the participant of subjective cognitive complaints, and findings from the screening neuropsychological battery, can be used for this determination by the investigative team. For example, the University of Washington CDR can be 0, but the CDR memory box score can be deemed to be 0.5 based on cognitive complaints at screening and meeting the MCI neuropsychological criteria.
 - General cognition and functional performance sufficiently preserved such that a diagnosis of dementia cannot be made by the site physician at the time of the screening visit.

- Abnormal memory function documented by scoring within the education adjusted ranges on the Logical Memory II subscale (Delayed Paragraph Recall, Paragraph A only) from the Wechsler Memory Scale-Revised.
 - For early MCI:
 - 9-11 for 16 or more years of education
 - 5-9 for 8-15 years of education
 - 3-6 for 0-7 years of education
 - For late MCI:
 - ≤ 8 for 16 or more years of education
 - ≤ 4 for 8-15 years of education
 - ≤ 2 for 0-7 years of education
- Age range: 55 years to 90 years.
- Sex distribution: all eligible men and women will be included, and no one will be excluded because of gender.
- Languages: fluent in English or Spanish. We have reliable, well-validated Spanish tests for all outcome measures.
- Participants without a known history of diabetes. If diabetes is diagnosed during screening (hemoglobin A1c [HbA1c] of 6.5% or greater) participants will be excluded. The main justification for this exclusion is the potential for these participants to be placed on other diabetes medications that may confound our study.
- General cognition and functional performance such that a diagnosis of dementia cannot be made at the time of screening based on DSM-V criteria.
- Vision and hearing must be sufficient for compliance with testing procedures.
- Must have a study partner to come to all appointments or be available by telephone at follow-up visits.

Study Partner Inclusion Criteria

- The study partner can provide an independent evaluation of functioning for a person enrolled in the MAP study as a participant.
- The study partner agrees to attend study visits with the MAP participant or be available by telephone.

5.2 EXCLUSION CRITERIA

- Use of metformin or any class of medication approved for the treatment of diabetes,¹³⁴ even if it is used for an indication other than diabetes (e.g. obesity), within 1 year of screening. These medications include GLP-1 agonists used for weight loss.
- Body mass index < 20 k/m².
- Metformin is contraindicated in persons with an estimated glomerular filtration rate (eGFR) of less than 30 mL/min. For persons with an eGFR of 30 to 45 mL/min, a reduction of the dose or discontinuation of metformin may be considered. It is also recommended that persons do not initiate metformin in this range. Thus, participants with eGFR < 45 mL/min will not be eligible to participate.
- The risk of lactic acidosis is increased in persons with liver disease and class III or IV congestive heart failure. Thus, persons with liver disease other than non-alcoholic-fatty liver disease or class III or IV congestive heart failure will not be eligible to participate due to the risks of side effects.

- A history of intolerance to metformin.
- History of cerebrovascular accident with residual neurological deficits.
- Moderate to severe depression, indicated by a score in the Geriatric Depression Scale of 9/15 or higher.
- Dementia diagnosis
- Lack of capacity to consent
- Participants with neurologic diseases associated with neurologic deficits on clinical examination.
- Participants with other current Axis I psychiatric diagnoses such as bipolar disorder or schizophrenia.
- Alcohol or substance abuse or dependence in the past 6 months.
- Use of medications rated as being the likely cause of cognitive impairment. These include benzodiazepines in dose equivalents greater than 2 mg daily of lorazepam, and regular use of prescription narcotics.
- Normal individuals without cognitive complaints.
- Participants with uncontrolled hypertension (systolic blood pressure \geq 160 mmHg or diastolic blood pressure \geq 95 mmHg).
- Participants with active cancer or a history of cancer within the last two years, with the exception of squamous or basal cell carcinoma of the skin.
- Participants who for any reason may not complete the study as judged by the study physician.
- Participants planning to move to another city or state during the duration of the study.
- Participants with a known history of diabetes. The rationale for this exclusion is persons with diabetes may already be on metformin or on other medications that increase insulin levels and could confound the trial.
- Participants with diabetes discovered on screening based on American Diabetes Association criteria using HbA1c (HbA1c of 6.5% or greater). Although metformin could be a first treatment of diabetes for these participants, addition of treatments for diabetes by physicians could confound the study.
- Use of any amyloid modifying treatment for AD such as lecanemab, either experimental or approved by the Food and Drug Administration, is exclusionary. Previous use of amyloid targeting therapy that was shown to be non-efficacious (e.g. solunazemab) is not exclusionary.
- Not able to undergo phlebotomy as reported by the participant or determined by the study coordinator or physician.
- Participants with known, suspected, or plan for becoming pregnant.
- The presence of a medical condition, and/or use of a medication and/or any substance, individually or in aggregate, that in the judgement of the study team, is the primary cause of cognitive impairment. For example, if hypothyroidism, cobalamin deficiency, or tertiary syphilis are reported or found during screening, they could be deemed as being likely contributors to cognitive impairment, and thus be exclusionary. Combinations of multiple medications with anti-cholinergic effects with or without other central nervous system depressants could also be considered as being causative of cognitive impairment and exclusionary.

Exclusion Criteria for MRI

Contraindications for MRI include inability to lie flat, claustrophobia, or presence of indwelling metal objects or implants that are not MRI compatible.

Exclusion Criteria for PET

History of adverse reactions to radiocontrast agents.

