The target sample are 326 (163 per arm) men and women aged 55 years to 90 years, with early or late amnestic mild cognitive impairment (aMCI), without dementia, without diabetes, with a body mass index (BMI) of 20 kg/m^2 or higher, not taking metformin, without contraindications to metformin use, and not taking any cognitive enhancers or medications that interfere with cognition. Biomarkers will not be used for the definition of aMCI. We will use the early aMCI and late aMCI criteria from the Alzheimer's Disease Neuroimaging Initiative (ADNI). The eligibility criteria, recruitment and retention strategies are described in detail in section 2.2 (Eligibility criteria). Persons without contraindications to MRI may undergo MRI, but inability or unwillingness to undergo MRI will not be a reason for exclusion. Participation will require the availability of a study partner (a person who knows the participant well), in order to answer questions about the participant in person or via telephone. Persons without contraindication to PET will also be invited to undergo amyloid and tau PET, independent of MRI.

Phase:	II /III
Description of Sites/Facilities Enrolling Participants:	There will be multiple sites in the United States chosen for their capacity to recruit, previous experience in Alzheimer's disease clinical trials, previous experience in National Institute on Aging's (NIA's) Alzheimer's Disease Cooperative Study (ADCS), and their affiliation with a local Clinical Translational Science Award (CTSA) funded by the National Center for Advancing Translational Sciences (NCATS).
Description of Study Intervention:	The trial will be preceded by a screening phase followed by randomization and a titration period in which extended-release metformin tablets or matching placebo (Glucophage XR, 500 mg/tablet [reduced mass]) will be titrated from 500 mg a day to 2000 mg a day in increments of 500 mg every 10 days. Enrolled study participants will undergo neuropsychological battery, clinical interviews, physical exam, and phlebotomy during four study visits at baseline, 6 months, 12-months, and 18-months. Brain MRI, amyloid PET, and tau PET will be conducted in up to 186 participants after the baseline visit and after the 18-month assessment. Adverse events and medication compliance will be checked every month. The placebo group will undergo the same study assessments and procedures, receiving placebo tablets rather than metformin.
Study Duration:	Up to 8 years

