2.3 RISK/BENEFIT ASSESSMENT

2.3.1 KNOWN POTENTIAL RISKS AND THEIR MITIGATION

Quality and risk management plan

To mitigate risks, an Integrated Quality & Risk Management Plan has been developed. The plan provides a summary of highest-scoring risks: delay in investigational products availability; failure to meet enrollment target; and high rate of missed assessments. In addition, the Risk Matrix provides details on risks to quality, along with mitigation strategies and risk scores.

Risks from metformin

Metformin is contraindicated in persons with an estimated glomerular filtration rate (eGFR) of less than 30 mL/min. For persons with an eGFR of 30 to 45 mL/min, metformin can be continued with caution but a reduction of the dose or discontinuation of the medication can be considered; in this range, it is also recommended that persons do not initiate metformin. Thus, participants with eGFR < 45 mL/min will not be eligible to participate. The risk of lactic acidosis is increased in persons with liver disease and class III or IV congestive heart failure. Thus, persons with liver disease other than non-alcoholic-fatty liver disease or class III or IV congestive heart failure will not be eligible to participate due to the risks of side effects. Non-alcoholic fatty liver disease is allowed given that it may benefit from metformin, unless it is at the cirrhosis stage.

Participants will be cautioned that IP be discontinued the day before any surgery or administration of contrast agents and may be resumed 48 hours after the procedure. We will monitor these contingencies on a monthly basis, and ad-lib as needed by the participant. We will also tell participants to avoid excessive intake or binge intake of alcoholic beverages. The Centers for Disease Control (CDC) define excessive alcohol intake as 15 drinks or more a week in men, and 8 drinks or more in women. The CDC defines binge

drinking as 5 or more drinks consumed on one occasion for men, and 4 or more drinks consumed in one occasion for women. The United States standard drink sizes are 12 ounces of 5% alcohol by volume (ABV) beer, 8 ounces of 7% ABV malt liquor, 5 ounces of 12% ABV wine, and 1.5 ounces of 40% ABV (80-proof) distilled spirits or liquor (e.g., gin, rum, vodka, whiskey).

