8.1 EFFICACY ASSESSMENTS

The study will have the following visits/calls: (1) telephone screening; (2) in person-screening and baseline study visit; (3) telephone calls for titration; (4) Follow up visits at months 6, 12, 18 months; (5) monthly calls between 6-month visits; (6) Brain Magnetic Resonance Imaging (MRI) at baseline and month 18. Primary and secondary clinical (non-MRI) efficacy data will be collected at baseline and the 6-month visits. Secondary MRI efficacy data will be collected at baseline and 18 months. The following is a brief description of these visits and the assessments included in these visits.

1. Telephone screening. We propose a 2-tier approach for screening, including telephone pre-screening followed by in-person screening. Telephone screening includes questions about inclusion and exclusion criteria including demographics, social history, medical history, contraindications to metformin, and medications. Study sites have the option of conducting a telephone cognitive screen such as the TICS to exclude persons with normal cognition.

Only persons who meet inclusion criteria and do not meet exclusion criteria are invited for in-person screening/baseline visit.

2. In-person screening and baseline study visit. In-person screening includes written informed consent, demographics, anthropometric measurements (height, weight, waist and hip circumference), vital signs (blood pressure and heart rate), EKG, laboratory tests (thyroid stimulating hormone [TSH], rapid plasma reagin [RPR], vitamin B12, complete blood count [CBC], basic metabolic panel [BMP], hepatic panel, lipid panel, and HbA1c), the neuropsychological battery, and a COVID-19 questionnaire. At the time of screening the tester will complete other assessments if the participant meets the neuropsychological criteria for MCI. All evaluations will be recorded in the eCRF, as applicable. If the participant meets all the inclusion criteria and has no exclusion criteria, the participant will be randomized and mailed a randomization kit with IP.

3. Telephone calls for titration. There will be 4 calls, one at the beginning of titration (one tablet a day), and 3 more calls every 10 days when the dose is increased by one tablet a day. During these calls, adverse events and tolerance will be documented.

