- During follow-up, if the participant develops dementia, indicated by a clinical dementia rating summary score of 1 as determined in the previous follow-up assessment. If the participant demonstrates capacity, he/she may consent; if the participant lacks capacity but wants to continue participation, a legally authorized representative will need to provide consent after the participant's assent. It is important to point out that this approach respects the participant's decision at baseline to participate in the study, when he/she had the capacity to consent.

Participants will be given three trials to respond to the UBACC. If after three trials they do not have a perfect score, they will be determined to lack capacity to consent. The determination of lacking capacity to consent will lead to exclusion at baseline, and to the need for a legally authorized representative to provide consent during follow-up. We expect that the contingencies described above will occur in less than 5% of the participants in the study, who will have mild cognitive impairment at baseline.

Medical history, medications

Detailed medical, surgical, and psychological history, and all medications utilized, including a judgment as to whether they affect cognition (positively or negatively) will be collected at baseline. Psychiatric history, current and past history of depression, current anxiety, alcohol and other substance use, head injury, hypertension, cardiac disease, thyroid disease, other major medical conditions, and surgery are evaluated at the baseline visit. A full medical history will be obtained only at the baseline visit. Any report of events, or side effects will prompt a full history and physical exam at follow-up visit. A COVID-19 questionnaire will be administered at every visit.

Physical Assessments (vital signs, anthropometric measures, brief neurologic exam)

A brief neurologic exam will be conducted at the in-person screening visit. Participants must also be assessed for signs of congestive heart failure, pulmonary, liver or renal disease as contraindications to

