10.1.10 PROTOCOL DEVIATIONS

A protocol deviation is any noncompliance with the clinical trial protocol, or Manual of Procedures (MOP) requirements. The noncompliance may be either on the part of the participant, the investigator, or the study site staff. As a result of deviations, corrective actions are to be developed by the site and implemented promptly.

It is the responsibility of the site investigator to use continuous vigilance to identify and report deviations within the required number of working days of identification of the protocol deviation. All deviations must be addressed in study source documents, reported to the NIA Program Official and Johns Hopkins TIC Data Coordinating Center. Protocol deviations must be sent to the reviewing sIRB per their policies. The site investigator is responsible for knowing and adhering to the reviewing sIRB requirements. Further details about the handling of protocol deviations will be included in the MOP.

Emergency deviations require reporting to the sIRB promptly after they occur

Emergency deviations are those occurring in an emergency situation, such as when a departure from the protocol is required immediately to protect the life or physical well-being of a participant. In such cases there is no time to prospectively seek the approval of the IRB. The sponsor and the sIRB must be notified as soon as possible, but not later than 5 days after the emergency situation occurred (21 CFR 812.150(a)(4)). Deviations of this nature are always considered to be unanticipated problems involving risks to participants or others (see JHM IRB Policy No. 103.6(b)).

Major, non-emergent deviations require approval by the sIRB before they occur

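### The liver exclusion in section 5.2 omits the cirrhosis limit that section 2.3.1 sets, so a site screening from the list alone could enrol someone the protocol bars

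*Protocol*

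**What the plan says.** The liver criterion in section 5.2 (Exclusion Criteria) opens with its reason: "The risk of lactic acidosis is increased in persons with liver disease and class III or IV congestive heart failure". The operative rule follows: "persons with liver disease other than non-alcoholic-fatty liver disease or class III or IV congestive heart failure will not be eligible to participate". The criterion ends there.

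Section 2.3.1 (Known Potential Risks and Their Mitigation), in its paragraphs on metformin, gives the same reason and the same rule and then adds one more sentence: "Non-alcoholic fatty liver disease is allowed given that it may benefit from metformin, unless it is at the cirrhosis stage".

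Section 8.1 makes the eligibility lists the gate to treatment: "If the participant meets all the inclusion criteria and has no exclusion criteria, the participant will be randomized".

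**The concern.** The two sections give different answers for the same candidate. Someone with fatty liver disease that has reached cirrhosis falls inside the unlimited exemption in section 5.2 and outside the limited one in section 2.3.1. Section 5.2 never says outright that cirrhotic disease is acceptable. The inconsistency arises by omission, but it sits in the list on which randomisation depends.

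What is at stake is individual safety. Section 2.2.2 calls lactic acidosis the most serious side effect of metformin, puts it below 0.01%, and says the trial avoids it by not giving the drug to people with contraindications. Eligibility screening is therefore the stated control for this risk, and here the written criterion is looser than the sponsor's own rule.

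There is also a consequence for trial conduct. Section 10.1.10 defines deviations broadly: "A protocol deviation is any noncompliance with the clinical trial protocol, or Manual of Procedures (MOP) requirements". Enrolling such a person would be a deviation, because section 2.3.1 is part of the protocol. A site working only from section 5.2 might not recognise it as one.

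**Working it through.** No arithmetic applies. The check is a comparison of text.

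**1. The two statements of the rule.**

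| Element | Section 2.3.1 | Section 5.2 |
|---|---|---|
| Reason: lactic acidosis | present | present |
| Liver disease excluded | present | present |
| Fatty liver disease exempt | present | present |
| Exemption ends at cirrhosis | present | absent |

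**2. Is the limit restored elsewhere?** The inclusion list in section 5.1 has no liver criterion. The remaining items in section 5.2 do not mention cirrhosis. In the protocol text at hand the word appears once, in section 2.3.1.

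**3. Does the neighbouring renal rule show how section 5.2 is meant to work?** The eGFR rule also appears in both sections, and its operative limit (below 45 mL/min is ineligible) is stated in both. The renal limit was carried into the list and the hepatic one was not.

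**4. Do other screening steps supply the limit?**

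- The synopsis describes a target sample "without contraindications to metformin use". This is general and names no stage of liver disease.
- Telephone screening in section 8.1: "Telephone screening includes questions about inclusion and exclusion criteria including demographics, social history, medical history, contraindications to metformin, and medications". This too is general.
- The in-person screen in section 8.1 includes a hepatic panel. No hepatic value is given as a bar to entry.
- The physical assessment in section 8.1: "Participants must also be assessed for signs of congestive heart failure, pulmonary, liver or renal disease as contraindications to" metformin. This prompts a look for liver disease, but a site that finds a fatty liver history then meets the unlimited exemption in section 5.2.

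Each step lowers the chance of a wrong enrolment. None states the rule in section 2.3.1.

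**5. Does the gap extend past randomisation?** Section 7.2 lets an investigator withdraw a participant who is found to meet an exclusion criterion, whether newly developed or previously missed. Cirrhotic fatty liver disease discovered later does not clearly meet any criterion in the list as written, although the separate adverse-event and medical-condition grounds in section 7.2 could still be used.

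**The case against.** The strongest reply is that the protocol should be read as a whole. Section 5.2 is silent where section 2.3.1 is explicit, both are binding, and together they yield one rule whose intent is not in doubt. The harm needs a site that uses section 5.2 in isolation and whose clinicians overlook cirrhosis despite the contraindication questions, the hepatic panel and the examination. After enrolment, section 2.3.1 provides hepatic testing every six months and stopping of the drug if a contraindication is suspected. Sections 8.3.4 and 8.3.8 name hepatic insufficiency among the conditions to look for or act on. The screening forms and the Manual of Procedures, which are not at hand, may already carry the limit.

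Much of this stands. The intent is clear, the safeguards are real, and whether any site would be misled depends partly on documents not seen. It does not remove the defect: no safeguard in the protocol states the limit, and the follow-up checks act only after exposure has begun.

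A practical point also stands. Section 1.3 expects data collection to finish by about 30 April 2026. Subtracting 18 months of follow-up puts the last randomisation at about the end of October 2024, roughly five months after version 2.0 of 21 May 2024. A later amendment may therefore govern little remaining enrolment.

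**Conclusion.** The concern holds. Sections 2.3.1 and 5.2 state the liver exclusion differently, and the list that governs randomisation has the version without the cirrhosis limit. The number of participants affected cannot be computed, because the protocol gives no frequency of cirrhotic fatty liver disease among candidates. It is probably small out of 326, and the general screening checks reduce it further. The consequence is confined to the safety of individual participants and the recognition of deviations. Sample size, power, type I error and the analysis are untouched.

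The wording difference is certain. That it could lead to a wrong enrolment assumes a site that relies on section 5.2 and screening materials that do not supply the missing limit. The correction should be made because the criterion concerns safety, the sponsor has already stated the intended rule, and the change is trivial.

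**What to change.** In section 5.2, qualify the fatty liver exemption so that it ends at cirrhosis, using the wording already in section 2.3.1. No new threshold or test is needed.

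Confirm that the telephone screen, the eligibility form and the Manual of Procedures carry the same limit, and send sites a short clarification if they do not. Because enrolment may be nearly complete or closed, also check the medical history of randomised participants for fatty liver disease, and refer any with cirrhosis to the medical monitor.

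The cost is one line at the next amendment, a check of the screening materials, and a limited query of medical history records.
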